6.0 Data Banking

6.1 Storage and access: Deidentified data will be stored in the PI's secure Box storage for future use by other researchers not on the research team. Data will be available 2 years following study completion ending 15 years after study start.

6.2 Data: Deidentified dataset.

6.3: Release or sharing: Outside researchers who request to use the deidentified data would have to have IRB approval documented with the PI prior to sharing of the dataset via a secure box file. Additionally, publishing of these data may be required. Federal funders (e.g. National Institutes of Health), granting agencies (e.g. Bill & Melinda Gates Foundation), and journal publishers (e.g. PLoS) increasingly require datasets be made publicly available—often immediately upon associated article publication. If this is the case, all data published will be fully de-identified.

7.0 Sharing of Results with Participants

- 7.1 General, group level (aggregate) survey results (e.g., means of participant scores) will be shared with participants and others as appropriate (e.g., academic research audiences, community groups). These group level study results will be conveyed in both peer-reviewed and lay publications (e.g., infographic/newsletter). The Community-Centered Dissemination Toolkit will be used to guide development of materials.

8.0 Study Duration

8.1 The duration for participant involvement in trial procedures is less than 1 year. Enrollment per wave is expected to take approximately 3 months. The duration anticipated to complete all study procedures and data analysis is approximately 5 years.

9.0 Study Population

9.1 Inclusion Criteria:

To achieve the proposed study aims, communities and human subjects from those communities will be recruited and data about operational procedures and costs will be collected.

Community site selection (see letters of support of interested site locations):

In order to be eligible to participate in this study, a community site (e.g., public housing hi-rise, low-income senior living residence) must meet the following criteria:

- (a) locale for low-income populations that experience difficulty in accessing healthy, affordable foods (e.g., public housing residences; low-income senior housing) or a community center in a low-income, low-food access (0.5 mile) census tract;
- (b) willingness to be randomized to the intervention or waitlist control;
- (c) located over 0.5 miles apart from other trial sites;
- (d) willingness to allow for recruitment and data collection to occur in onsite community rooms;

Process for initial contact with sites:

[name] at The Food Group with the Twin Cities Mobile Market regularly receives calls from site locations across the Twin Cities that may be interested in having the mobile market come. As these calls come in, she will provide information on the mobile market service in general and also that there is a research study opportunity. She'll provide the sites a site flyer. She will connect any interested sites with the Mobile Market researchers for specific questions related to the research, if any, prior to the formal conversation, as outlined in the attached site screening script (below).

Flyer for site recruitment: We have created a flyer for sites (attached) interested in mobile market service study to provide information on the mobile market research study. This site flyer would serve as a preview to a more formal conversation about being both a mobile market site and research site. It should be noted that the site recruitment flyer lists the contact information for Co-Investigator [name] given her position of regularly receiving this type of call at the Mobile Market currently. She will refer sites to the researchers for research specific questions as they arise prior to a formal conversation as outlined with the screening script.

Site screening script:

SOCIAL PROTOCOL (HRP-580)

PROTOCOL TITLE: Mobile Food Market Cluster Randomized Trial

VERSION DATE: 1/5/2023

For sites that may be interested, a research team member and Co-Investigator [name] will go through a formal conversation using the site screening script to guide the conversation. Please see the site screening script attached.

When sites would like to join:

If an interested site were to be interested, eligible and decide to participate, a letter of support would be written documenting this decision. This letter of support will be provided to the UMN IRB following signature.

Sites meeting site eligibility criteria will be recruited in three waves, with 4 sites in wave 1, 4 sites in wave 2, and 4 sites in wave 3. After baseline data collection for each Wave, stratified randomization of sites by type (e.g., randomization within public housing, low-income senior living sites) will be conducted to ensure balance between groups. See support letters from sites on the market waitlist meeting the aforementioned criteria.

Human subject recruitment will occur in the participating communities.

In order to be eligible to participate in this study, an individual must meet the following criteria:

- (a) being aged 18 years or older;
- (b) identifying as the primary food shopper in their household;
- (c) being able to speak English or American Sign Language (ASL);
- (d) living within a half mile of the community site location; and
- (e) reporting to be likely or somewhat likely to shop at the market in response to:
“how likely would you be to shop regularly at the Twin Cities Mobile Market if it came to your neighborhood each week (response options: likely to unlikely).
- (f) willing and able to participate in all study data collection activities
 - Please note: we may be amending these inclusion criteria and this protocol and all documents to include individuals who speak other languages once the community sites are selected and the other languages are known.

9.2 Exclusion Criteria: An individual who meets any of the following criteria will be excluded from participation in this study:

- (a) planning to move in the next 12 months
- (b) not currently shopping at the mobile market
- (c) not having a phone number or mailing address
- (d) presence of a condition or abnormality that would prohibit participation in the study or the quality of the data

9.3 Screening: Screening will occur in person or via phone using the eligibility screening script (attached). Participants will self-report answers to these questions.

Participants will be asked to provide verbal consent prior to conducting the initial

screen. Participants who consent to proceed with the screening process will be documented by study staff.

If participants are found to be potentially eligible after phone screening, they will be invited to the study for a full written consent process that covers the remainder of the study, as described in this protocol.

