fresh, frozen and canned fruits and vegetables, whole grains, dairy / dairy substitutes, proteins (e.g., frozen meat/fish, beans, eggs), and dry goods (e.g., cooking oil, spices). Foods will be priced below the cost of local supermarkets (~10% below) and purchases can be made with cash, SNAP/EBT, or credit/debit. The state funded Market Bucks program will provide a dollar-for-dollar match, up to \$10, for produce purchases made with SNAP benefits. Customers will be able to enroll in a “Market Members” loyalty card program that provides incentives for shopping more frequently (e.g. \$5 off every third trip) and all customers will be asked at the point of sale if they are a Member. Community engagement will continue during this time; market staff will check in with site partners regularly to ensure smooth service, addressing any challenges and capitalizing on opportunities (e.g., community events to promote the market) in real time. Intervention site participants will be contacted monthly (e.g., sent a newsletter on the market offerings/sales) in addition to retention contacts described above.

[figure not shown]
As a note, this the start-up and implementation of the mobile market occurs at new Mobile Market sites that are starting up or that are receiving ongoing service unrelated to the trial as well – thus, this step (aside from the randomization) is not different than would/does occur normally with mobile market start-up at a new location.

Waitlist control. Sites randomized to the waitlist will not receive market service prior to follow-up data collection. After follow-up Wave 1 data collection, Wave 1 waitlist sites will participate in community engagement and then receive the market. After follow-up Wave 2 data collection, Wave 2 waitlist sites will do the same. After follow-up Wave 3 data collection, Wave 3 waitlist sites will do the same. The use of a waitlist control was purposeful and informed by our community partners. We will be in communication with waitlist site participants during the 6-month implementation period at the intervention sites, as described above to ensure up-to-date contact information and to facilitate engagement/retention.

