Baseline Data collection: The consent forms will be mailed to interested and eligible participants in advance of the baseline data collection visit. The process of informed consent will take place at baseline data visits in a private and confidential space [using a privacy screen if needed]. Data collection will occur at baseline (after site recruitment but before site randomization is known to sites, participants, research staff, the PI, and non-statistician University co-investigators) and again at follow-up (after 6 months of mobile market service at sites randomized to the intervention) for all sites. Data collection will occur simultaneously at intervention and waitlist sites to minimize the threat of temporal trends (e.g., changes in community, policy, or economic climate). Data collection will occur onsite or in nearby community locations and over the telephone. Mobile market purchasing data collection will occur during and after the intervention through the end of data collection for participants at sites randomized to receive the mobile market first. Implementation process data collection will occur throughout the trial and participant process data collection will occur after the 6 month implementation of the mobile market intervention. If sites do not have adequate privacy, we will create a private space with privacy screens. The surveys will be completed by participants using a Health Sciences registered iPad using a secure web-based REDCap survey. In case of technical failure, paper-pen back-up surveys will be available. If this is needed, paper-pen surveys will be entered into a secure REDCap database¹¹⁸ by two study staff and verified for accuracy. Diet recall data will be entered in Nutrition Data System for Research (NDSR) software by trained staff. The data will be stored on

SOCIAL PROTOCOL (HRP-580)

PROTOCOL TITLE: Mobile Food Market Cluster Randomized Trial

VERSION DATE: 1/5/2023

secure University laptops and backed-up to secure BOX data servers. Paper files will be stored in secured, locked file cabinets. See the table below for a broad overview of timeline of data collection and measurement. Details for each of the measures is provided below the table.

	Screening	Baseline	6 month intervention	Follow-up data collection	Qualitative interviews
Eligibility and study interest	x				
Informed Consent		x			
Diet Quality (measured with 3 dietary recalls - one in person, and 2 in the next three weeks by phone)		x		x	
Food security		x		x	

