Intervention/waitlist control: The intervention, Twin Cities Mobile Market service will be provided in the communities recruited for the trial. This service will be the same service provided to other community sites with ongoing Mobile Market service. Service will be available to anyone in the community regardless of trial enrollment. Intervention sites will receive mobile market service following two months of strategic community engagement. Waitlist control sites will receive mobile market service after follow-up data collection for the wave is complete. More detail is provided in IRB protocol section 4.1.

Data analysis: Data will be analyzed by research staff to answer study related research questions and to determine the individuals who are the high and low adopters of mobile market shopping for qualitative interviews related to the study's third aim. See details in IRB protocol section 17.

The following actions will be taken if a participant misses a study visit:

- The study team must attempt to contact the participant and reschedule the missed visit as soon as possible, counsel the participant on the importance of maintaining the assigned visit schedule, and ascertain whether the participant wishes to and/or should continue in the study.
- Before a participant is deemed lost to follow-up, the investigator or designee must make every effort to regain contact with the participant, where possible, by text, email, telephone calls, and if necessary, a certified letter to the participant's last known mailing address. These contact attempts will be documented in the participant's contact log. Should the participant be unreachable for 5 consecutive attempts by phone or text without response/reply followed by a certified letter without response, the participant will be considered to have withdrawn from the study.

5.4 Follow-Up: The data collection process will be identical to that of baseline data collection with a few exceptions, noted below. There is not long-term follow-up data collected.

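### Does a site spacing of just over half a mile, with half-mile catchments, let waitlist participants dilute the comparison enough to need a new rule?

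*Combined protocol and SAP*

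**What the plan says.** Site criterion (c) in section 9.1 requires each site to be "located over 0.5 miles apart from other trial sites". Individual criterion (d) in the same section requires "living within a half mile of the community site location"; section 26.1 restates this with reference to the closest site. No criterion in 9.1 or 9.2 mentions living near another trial site. Screening under 9.3 rests on the participant's word ("Participants will self-report answers to these questions"), although 9.2 excludes anyone "not having a phone number or mailing address".

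The waitlist restriction in section 4.1 applies to the site and not to where its participants shop. Section 5.3 says of the market: "Service will be available to anyone in the community regardless of trial enrollment". Stops also accumulate over the waves: "After follow-up Wave 1 data collection, Wave 1 waitlist sites will participate in community engagement and then receive the market". On where sites come from, section 9.1 says that the mobile market "regularly receives calls from site locations across the Twin Cities".

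The process-measures table in section 5.2 provides for measuring contamination by a follow-up survey and by Mobile Market trips recorded on the purchase forms. Section 17.3 makes intention to treat the primary framework and adds dose-adjusted analyses.

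**The concern.** The two distances look mismatched. A half-mile catchment around each site needs a mile between sites if no home is to fall in two catchments, and the plan asks for only half of that. A waitlist participant living in the shared area could walk to a same-wave intervention stop during the six months between baseline and follow-up, which is the period over which the primary change in HEI-2015 is measured. Enrolment favours people who say they are likely to use such a market, so the opportunity might well be taken.

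Any benefit gained that way would shrink the intention-to-treat difference towards zero and cost power. Measuring contamination afterwards does not undo this in the primary contrast. Stops from earlier waves matter less, because their use before baseline is partly reflected in the baseline value.

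**Working it through.** **Inputs from the documents.** Minimum spacing 0.5 mile and catchment radius r = 0.5 mile (9.1); 12 sites, 4 per wave, 22 participants per site (5.1); analysed sample 224, ICC 0.01, 15% attrition and 5.0 HEI points at 80% power (11.1); SD 12, design effect 1 + (m − 1) × ICC and two-sided 5% (17.2).

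**Assumptions.** One neighbouring site, homes spread evenly over the catchment, six control sites of equal size, and a 2:2 split within a wave. The share of participants living off-site is not given; a quarter, a half and all are shown.

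**1. The plan's own power.** m = 224/12 = 18.67. Design effect = 1 + 17.67 × 0.01 = 1.177. Effective n per arm = 112/1.177 = 95.2. Standard error = 12 × √(2/95.2) = 1.739. The ratio 5.0/1.739 = 2.874 gives power 81.6% by the two-sample t-test, consistent with the 80% stated in 11.1.

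**2. Geometry.** The overlap of two circles with centres d apart is 2r²·arccos(d/2r) − (d/2)·√(4r² − d²). Let s be its share of πr². If each person is assigned to the closest site, as in 26.1, the share becomes (s/2)/(1 − s/2).

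| d (mile) | Share s | Closest-site share |
|---|---|---|
| 0.5 | 39.1% | 24.3% |
| 0.75 | 14.4% | 7.8% |
| 1.0 | 0% | 0% |

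Someone who lives at the waitlist site itself is more than 0.5 mile from every other trial site by criterion (c). Only off-site residents can be affected.

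**3. Exposed controls, one split pair at the limit.** f = share × off-site fraction / 6. The diluted effect, if every exposed control gets the full benefit, is 5.0 × (1 − f).

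| Off-site fraction | f | Diluted effect | Power |
|---|---|---|---|
| 0.25 | 1.0–1.6% | 4.95–4.92 | 80.8–80.3% |
| 0.5 | 2.0–3.3% | 4.90–4.84 | 80.0–79.0% |
| 1 (community center) | 4.1–6.5% | 4.80–4.67 | 78.4–76.2% |

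With a quarter off-site, 22 × 0.25 × 0.243 = 1.3 to 22 × 0.25 × 0.391 = 2.2 people at that site are exposed. With the alternative inputs in 17.2 (SD 11.2, ICC 0.0004), power goes from 91.2% to 90.7–90.3%.

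**4. Less extreme assumptions.** With two of four sites per arm, a given pair is split with probability 1 − 1/3 = 2/3 (up to 1 if the pair forms its own stratum). If exposed controls get half the effect (assumed), f is multiplied by 2/3 × 1/2 = 1/3. With a quarter off-site, f = 0.34–0.54% and power is 81.3–81.2%, a loss of 0.3–0.4 points. With everyone off-site, f = 1.35–2.17% and power is 80.5–79.9%.

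**5. What an exclusion would do.** Suppose anyone within half a mile of another trial site were excluded. For a pair at the limit with even spread, the mean distance from eligible homes to the other stop rises from 0.57 to 0.72 mile, and 58% of those still eligible live within 0.75 mile of it. With a quarter off-site, the pair loses 2 × 1.3 to 2 × 2.2 enrolled people, or 2.3 to 3.7 analysed after 15% attrition. If they are not replaced, n falls to 221.7–220.3 and power to 81.3–81.0%, a cost of 0.3–0.5 points, which matches the gain in step 4.

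**The case for a change.** The best case for acting is that the gap is in the text and is cheap to close. Nothing else in the eligibility criteria prevents the overlap: the current-shopping criterion in 9.2(b), however it is read, concerns use at enrolment and not later use of a new stop. Recruitment includes an informational visit by the market to every site (12.1), so waitlist participants will know of it. Loyalty-card tracking covers intervention participants only; for controls, contamination rests on self-report and four-week purchase forms. Same-wave sites are known when participants are recruited. A mailing address is already required and "The consent forms will be mailed to interested and eligible participants in advance of the baseline data collection visit", so an address check would add little work. Finally, the quarter-off-site assumption suits housing blocks, while criterion (a) also admits community centers, where power could fall to between 78.4% and 76.2%.

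Much of this stands. The overlap is permitted, the cost is small, and the community-center figure is correct on its assumptions. But that figure needs a waitlist community center at the very limit, an intervention site of the same wave as its neighbour, and the full benefit in every exposed control. The eligible site types named first in 9.1 are residences, and recruitment through resident meetings and door hangers reaches people who live on site. Half a mile is no natural limit on shopping trips, so a new cut-off there would move the boundary rather than close the route, and the 24 stops already running would stay outside it.

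**Conclusion.** The observation is correct and no change follows. Sections 9.1(c) and 9.1(d) allow catchments to overlap for sites between 0.5 and 1.0 mile apart, but no distances are given, and at a mile or more the overlap is zero.

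With a quarter of participants off-site, the worst case for one pair at the limit is about 0.8 to 1.3 power points. Allowing for the chance of a split and half the effect, it is 0.3 to 0.4 points, before allowing for the chance that no such pair exists. The bias runs towards no difference, so it cannot create a false benefit, and contamination is already measured, with dose-adjusted analyses alongside. The obvious remedy costs about what it gains unless the excluded volunteers are replaced.

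Spacing sites more widely would narrow the pool of willing sites, so the present rule is a fair trade-off. The conclusion rests on one close pair, evenly spread homes and mainly residential sites; several close same-wave pairs, clustered homes or community-center sites would make the loss larger.

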Full-service mobile markets are viable and sustainable. While some states like Minnesota are on the forefront of supporting mobile markets through funding legislation,⁵⁸ most mobile markets nationwide are grant funded and/or supported by philanthropic donations. As such, many produce-only mobile markets close due to financial non-viability or when external funding ends.^{56,57} Full-service mobile markets also rely on a robust non-profit infrastructure and organizational partnerships to source foods at wholesale cost. However, aligned with recommendations from research, full-service mobile markets address viability and sustainability in two important ways.^{52,55} First, full-service mobile markets’ operational costs are supported by the sales of all food groups, thus, offsetting operational expenses more efficiently than through fruit and vegetable sales alone. Our formative work showed 50% of full-service mobile market sales were for fruits and vegetables and the other 50% were for protein, dairy, grain, and dry good purchases.⁵⁹ Second, selling only produce reduces reach and deters shopping because customers must go elsewhere to purchase other essential foods.^{52,55} Therefore, the full-service mobile market can increase sales and reach by providing one-stop shopping, and thus has greater potential for sustainability.^{52,55} Our study will evaluate the impact of an established and thriving non-profit full-service mobile market model on diet quality, food insecurity, and food purchases while also studying factors impacting market shopping adoption.

The full-service mobile market to be evaluated has high potential to improve diet, food security, and food purchase patterns. *The full-service Twin Cities Mobile Market was launched in 2014 in response to community need for affordable healthy food access. It operates two city buses retrofitted into grocery stores, with food display shelving, refrigeration, freezers, and shopping carts. The market serves 24 community sites weekly⁶⁰ and is operated by a 501c3 non-profit organization. Operation costs are covered in part by revenue generated from food sales, with a subsidy provided by the market’s non-profit infrastructure.*

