4.0 Study Intervention(s)/Interaction(s)

4.1 Description:

Intervention and waitlist control. Following baseline participant data collection, sites will be randomized to receive the full-service mobile market intervention or serve as the wait list control.

The Full-Service Mobile Market start-up involves two key components.

(1) Initial community engagement: Prior to randomization, community sites will begin engagement activities aligned with CBPR best-practices.¹¹⁵⁻¹¹⁷ These activities include regular meetings with site location staff to develop logistical plans for research activities and market intervention. Following randomization, site group assignment will be revealed for participants and the UMN research team after baseline data collection for the wave is complete, continued site engagement will occur to finalize logistics, including selection of time for the weekly market stop. Resident meetings will be held to introduce how the market works (e.g., when it will come, foods / prices to expect, payment forms accepted). The market schedule will be advertised in community sites (e.g., elevators, community rooms, resident newsletters). Based on our ongoing work, this initial community engagement takes two-weeks to two months, is critical to launching new sites, and is essential for building/maintaining rapport and trust. These activities will be repeated for waitlist sites after follow-up data collection in each Wave.

As a note, this community engagement occurs at new Mobile Market sites that are starting up unrelated to the trial as well – thus, this step (aside from the randomization) is not different than would/does occur normally with mobile market start-up at a new location.

(2) Full-service mobile market implementation (the beginning of the intervention): After initial community engagement, the intervention will begin. Specifically, the market will visit intervention sites weekly. The market will carry items from all food groups including

SOCIAL PROTOCOL (HRP-580)

PROTOCOL TITLE: Mobile Food Market Cluster Randomized Trial

VERSION DATE: 1/5/2023

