12.0 Recruitment Methods

SOCIAL PROTOCOL (HRP-580)

PROTOCOL TITLE: Mobile Food Market Cluster Randomized Trial

VERSION DATE: 1/5/2023

12.1 Community and Participant Recruitment process:

Community recruitment process:

When: After grant is awarded. Process will begin approximately 2-5 months into the grant.

Where: At/around the Twin Cities in low-income/low food access communities meeting site inclusion criteria.

Strategies: Mobile market staff will work with their ongoing community partners, sites on their waitlist (interested in service when capacity to expand is available), and new potential partners to recruit sites meeting inclusion criteria to receive mobile market service as part of the trial (depending on randomization, as either intervention or waitlist control sites). While the sites will be specifically recruited for the trial, the mobile market service at these sites will be normal mobile market service (i.e., the same service that is currently ongoing at other community site locations that are not part of the trial). At the trial site locations of this trial, anyone will be able to shop at the mobile market, not just those enrolled in the trial.

Participant recruitment process:

When: After recruitment of community sites

Where: At/around the community sites recruited for the trial before randomization of communities to mobile market service or waitlist control is known to sites, participants, research staff, the PI, and non-statistician University co-investigators.

Strategies:

- working closely with community site staff to get the information to community members
- posting flyers and tabling in central locations around recruited site locations
- attending resident meetings (e.g., resident council in public housing buildings)
- sending trial information along with community newsletters/ updates
- bringing the mobile market to each site for an informational event

Retention strategies:

- providing contact throughout the study to retain up-to-date contact information (e.g., calls/text messages/emails, reminder letters, seasonal cards, monthly newsletters),
- continuing to collect data in a convenient location
- providing culturally and linguistically competent staff

SOCIAL PROTOCOL (HRP-580)

PROTOCOL TITLE: Mobile Food Market Cluster Randomized Trial

VERSION DATE: 1/5/2023

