Full-Service Mobile Market Intervention Risks and Protections: The full-service mobile market intervention is a community level intervention that already exists in the Twin Cities metropolitan area (there are 24 current weekly stops). While the full-service mobile market intervention will be newly available to the community sites participating in the proposed trial, the risk of participation in the mobile grocery store is minimal and equal to participation in mobile market service not associated with the trial. For example, participants of the trial will have the same opportunity to use the mobile market as will their neighbors who may or may not be in the trial. In addition, the mobile market staff on the full-service mobile market will not know (or have access to data to know) whether customers are participants in the trial or not; thus, accidental disclosure of study participation by staff will not be possible.

14.2 Reproduction Risks: Not applicable.

14.3 Risks to Others: Not applicable.

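### The half-mile spacing rule covers only other trial sites, so off-trial stops of the same market may run or open near a waitlist site; a minor gap, cheap to close

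*Combined protocol and SAP*

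**What the plan says.** - **Site spacing.** Section 9.1(c) requires each site to be "located over 0.5 miles apart from other trial sites". Site criteria (a), (b) and (d) do not mention other stops of the market.
- **Catchment.** Participants qualify by "living within a half mile of the community site location" (section 9.1(d), individual criteria).
- **Existing off-trial service.** Section 2.1 states "The market serves 24 community sites weekly", and section 14.1 repeats the figure.
- **New off-trial service.** Section 4.1 notes that "this community engagement occurs at new Mobile Market sites that are starting up unrelated to the trial as well".
- **Open access.** Section 5.3: "Service will be available to anyone in the community regardless of trial enrollment".
- **Waitlist protection.** Section 4.1: "Sites randomized to the waitlist will not receive market service prior to follow-up data collection". This concerns service at the waitlist site; it is silent on stops nearby.
- **Current shoppers.** Section 9.2(b) addresses current use of the market at enrolment. Placed among the exclusions, its wording is reversed: read literally, it excludes people who do not shop there.
- **Contamination.** The process-measures table in section 5.2 collects self-reported market use at follow-up, and market trips from the purchase forms at baseline and follow-up. Section 17.3 makes the primary analysis intent-to-treat and adds dose-adjusted analyses.

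**The concern.** The half-mile separation between trial sites shows that the plan regards proximity as a route for contamination. Section 5.3 describes the service at trial sites as the same as that at the market's other stops. A waitlist participant near an off-trial stop therefore has access to much the same shop as one near an intervention stop, yet the rule covers only the second case.

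The exposure that matters is the kind that begins between baseline and follow-up: a new off-trial stop opening near a waitlist site, or participants starting to use a stop already nearby. The second is conceivable because section 9.1(e) enrols people who say they are likely or somewhat likely to shop at the market. The window is up to about eight months (as much as two months of engagement plus six of service, section 5.1), plus data collection.

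Any such use would improve diet in the control arm, if the market works, and pull the HEI-2015 difference toward zero. Contamination data can describe this afterwards but cannot remove it from the intent-to-treat estimate.

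**Working it through.** **Inputs**
- 264 enrolled, 15% attrition, 224 analysed, 12 clusters, a 5.0-point difference and 80% power: section 11.1.
- SD 12, ICC 0.01, two-sided 5% test, individual-level t-test with inflation factor 1 + (m − 1) × ICC: section 17.2.
- Six waitlist sites: 132 per group (section 17.2) divided by 22 per site (section 5.1) = 6.
- Number of exposed waitlist sites and their use of the off-trial stop: **not in the documents, assumed below.**

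**Step 1. Reproduce the plan's figure.**
- Average cluster size: 224/12 = 18.67.
- Design effect: 1 + 17.67 × 0.01 = 1.177.
- Standard error of the difference: 12 × √(4 × 1.177/224) = 1.74.
- Noncentrality: 5.0/1.74 = 2.87. A two-sided 5% t-test on 222 df gives power of **81.6%**, in line with the stated 80%.

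**Step 2. Dilute the difference.** Let e be the number of exposed waitlist sites and u the use of the off-trial stop relative to use at an intervention site. If the effect is proportional to use and sites are of equal size:

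difference = 5.0 × (1 − (e/6) × u)

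| Exposed waitlist sites | Relative use | Difference (HEI points) | Power |
|---|---|---|---|
| 0 | – | 5.00 | 81.6% |
| 1 | 25% | 4.79 | 78.3% |
| 1 | 50% | 4.58 | 74.7% |
| 1 | 100% | 4.17 | 66.5% |

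For example, one site at 50% use gives 5.0 × (1 − 0.5/6) = 4.58.

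**Step 3. Check against section 17.2.** That section assumes 20% attrition and 5.5 points. With 264 × 0.8 = 211 analysed and m = 20, the design effect is 1.19 and undiluted power is 86.0% by the method described. One exposed site gives 83.0%, 79.6% and 71.7% at 25%, 50% and 100% relative use. The losses are similar (3.0, 6.4 and 14.3 points, against 3.3, 6.9 and 15.1 in Step 2). Separately, sections 11.1 and 17.2 differ on attrition and detectable difference for the same 264 participants and need to be reconciled.

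**The case against.** **Existing stops are mostly background.** A reader might infer that a waitlist site near one of the 24 running stops is in effect a treated site analysed as control. The documents do not support that. The primary outcome is within-person change, so a stop that operated throughout contributes a constant background. On its evident intention, 9.2(b) removes those already shopping there. Only use that starts or grows after enrolment affects the contrast. This objection stands, and it limits the point mainly to new stops and new users.

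**Nearness is not documented.** Section 12.1 says "Mobile market staff will work with their ongoing community partners", but the same sentence goes on to sites on the market's waitlist and to new partners, and an existing partner is not a neighbouring stop. That section also implies that expansion depends on capacity, and section 2.1 describes two buses. Section 4.1 shows that off-trial start-ups happen but gives no rate or location. This also stands: the risk is possible, not shown.

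**A rule may exist elsewhere.** The revision history says that general criteria for receiving the market were separated from the research criteria on the site screening script. That script was not available for this review and could contain a spacing rule. The protocol's own criteria do not.

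**Full use is severe.** Setting relative use at 100% equates an incidental stop with weekly service at the site plus resident meetings, local advertising, newsletters and loyalty enrolment, and it treats every participant at the site as exposed. It is a bound, not an expectation.

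**Contamination is measured.** True, and useful for interpretation, but it does not repair the intent-to-treat comparison.

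**Conclusion.** The gap in 9.1(c) is real as written, and closing it is a minor, inexpensive improvement. The plan allows a trial site near an off-trial stop, and allows a new off-trial stop to open near a waitlist site before that wave's follow-up. The main risk is exposure that begins during the control period.

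If one of six waitlist sites were exposed, the loss from 81.6% power would run from about 3 percentage points (25% relative use) to about 15 (100%, the upper bound for one site). This rests on assumed exposure, an effect proportional to use, and equal site sizes. Two sites at full use would give 3.33 points and 47.9% power, but nothing in the documents indicates that situation, and it should not be read as a forecast. Nor do the documents establish that contamination will occur, or that no rule exists in the screening script.

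**What to change.** 1. **Section 9.1(c):** extend the half-mile minimum so that it applies to any active Twin Cities Mobile Market stop as well as to other trial sites. If the site screening script already says this, bring the rule into the protocol text.
2. **Section 4.1, waitlist paragraph:** state that, where feasible, the market's route planning will avoid opening off-trial stops within 0.5 mile of a waitlist site until that wave's follow-up data collection ends, and that any exception will be recorded.
3. **Section 9.2(b):** correct the reversed wording, since the limited role of existing stops depends on it.

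**Cost.** Wording, plus a check of each candidate site against the market's own stop list; the market's representative is a co-investigator who is already involved in route planning. A few candidate sites may become ineligible, and an off-trial start-up near a waitlist site may be delayed for some months. An absolute ban on such openings would withhold routine service from people outside the research, so the where-feasible form is preferable.

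**Limit.** Participants may live up to 0.5 mile from their site, so a stop just beyond the limit can still be close to some of them. The rule reduces this exposure but does not eliminate it.
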